4.2.2 Study Schedule

The Schedule of Evaluations in [Appendix I](#) provides details on the study schedule, the permitted windows for completing the visits, and the evaluations to be performed at each visit. The visit schedule is based on intervals of time after each study injection ([Appendix I](#)). The clinicians will discuss the target dates and timing of the study vaccination(s) and sample collections with each subject before completing enrollment to help ensure that subjects can comply with the projected schedule.

After enrollment, deviations from the visit windows are discouraged and will be recorded as protocol deviations but are permitted at the discretion of the PI (or designee) in the interest of completing the vaccination schedule and obtaining subject safety and immunogenicity evaluations.

4.2.3 Enrollment

The study has staged enrollment with required interim safety reviews, as described in Section 4.3, for dose escalation, continuing enrollment, and second product administration. The first three subjects of Groups 1 and 2A will be enrolled with no more than one subject per day.

Subjects will be stratified by age into Group 2A, 2B, 2C, and 2D.

The pharmacy database will be set up prior to opening the study to accrual. The group assignment is known to the staff and subject before completing the electronic enrollment into the study on Day 0. Any subject who receives at least one study injection will be expected to continue with follow-up through the end of the study.

4.2.4 Acceptable and Effective Methods of Birth Control

Women of reproductive potential are required to agree to use an acceptable and effective method of birth control beginning 21 days prior to enrollment and continuing through end of study.

Acceptable and effective methods of birth control for women of reproductive potential in this study include: abstinence (no sex) with male partners, birth control pills or patch, condoms, Medroxyprogesterone acetate (MPA) injection, diaphragm or cervical cap, intrauterine device (IUD), Implant (Nexplanon®), NuvaRing®, partner has vasectomy, or use of spermicides.

4.2.5 Vaccine Administration

All study injections will be completed according to the assigned group and will be administered IM in the deltoid muscle. Scheduled blood collection must be completed before vaccinations.

On the injection day (prior to injection), study subjects will be clinically evaluated and samples will be collected as per Schedule of Evaluations ([Appendix I](#)). A subject who arrives at the clinic with fever or evidence of an acute illness that precludes administration of the vaccine may be rescheduled within the allowed study visit window.

Pregnancy test results for women of reproductive potential must be obtained on each injection day prior to the study injection and the results must be negative to proceed.

When choosing an arm for injection, clinicians should consider whether there is an arm injury, local skin problem or significant tattoo that precludes administering the injection or will interfere with evaluating the arm after injection.

Subjects enrolled in Group 1 will be observed for a minimum of 1 hour following the injection. Vital signs (temperature, blood pressure, pulse and respiratory rate) will be collected at least 1 hour after the injection, prior to subject departure from the clinic.

Subjects enrolled in Group 2A, 2B, 2C, and 2D will be observed for a minimum of 30 minutes following each injection; vital signs will be collected after at least 30 minutes.

For all subjects, the injection site will be inspected for evidence of local reaction following the observation period.

In keeping with the NIH CC policy and good medical practice, acute medical care will be provided to subjects for any immediate allergic reactions or other injury resulting from participation in this research study.

4.2.6 7-Day Solicited Reactogenicity and Follow-up

Subjects will be given a “Diary Card” to use as a memory aid, on which they can record temperature and symptoms daily for 7 days after each injection. Subjects will be trained and encouraged to use the secure electronic database but will have the option to complete a paper diary card. When the diary card parameters are recorded directly by the subject in the electronic database, the subject’s electronic record will be the source for these data. When collected on paper, the paper diary card will be the source document. When neither paper nor electronic diary is available from the subject, the study clinician will document the source of reactogenicity information recorded in the study database.

The solicited signs and symptoms on the diary card will include the following parameters: unusually tired/feeling unwell, muscles aches (other than at injection site), headache, chills, nausea, joint pain, and pain/tenderness, redness, swelling, skin lesions at injection site. Subjects will also record the day’s highest measured temperature and measurement of largest diameter for redness and swelling at injection site.

Follow-up on subject well-being will be performed by telephone on the first day following all injections and by clinic visits as shown in the Schedule of Evaluations ([Appendix I](#)).

Events following any study injection that may require clinical evaluation include rash, urticaria, fever of 38.5°C (Grade 2) or higher lasting greater than 24 hours, or significant impairment in the activities of daily living. Additionally, other clinical concerns may prompt a study visit based on the judgment of a study clinician.

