4. STUDY DESIGN AND CLINICAL PROCEDURES

This is a Phase I, open-label, dose escalation study to evaluate the dose, safety, tolerability, and immunogenicity of the VRC-FLUNPF099-00-VP vaccine in two dose regimens in healthy adults. The study schema is shown in **Table 1**. The hypotheses are that the vaccine is safe, well-tolerated, and will induce an antibody response to the stem of influenza virus subtype H1. The

study will be conducted by the VRC Clinical Trials Program at a single site in the NIH Clinical Center (NIH CC), Bethesda, MD.

Table 1: Study schema:

VRC 321 Vaccination Schema				
Group	Age	Subjects	Day 0	Week 16
1	18-40	5	20 mcg	
2A	18-40	12	60 mcg	60 mcg
2B	41-49	12	60 mcg	60 mcg
2C	50-59	12	60 mcg	60 mcg
2D	60-70	12	60 mcg	60 mcg
Total		53*	*Enrollment up to 70 is permitted if additional subjects are needed for safety or immunogenicity evaluations.	

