5. SAFETY AND ADVERSE EVENT REPORTING

5.1 ADVERSE EVENTS

Adverse Event (AE) - Any untoward medical occurrence in a human subject, including any abnormal sign (for example, abnormal physical exam or laboratory finding), symptom, or disease, temporally associated with the subject's participation in research, whether or not considered related to the subject's participation in the research. In the context of FDA-required reporting, an AE means any untoward medical occurrence associated with the use of a drug in humans, whether or not considered drug related.

Each AE will be graded according to the Toxicity Grading Scale for Healthy Adult and Adolescent Volunteers Enrolled in Preventive Vaccine Clinical Trials, Food and Drug Administration Guidance – September 2007 ([Appendix II](#)). The following guidelines will be used to determine whether or not an AE is recorded in the study database:

- Solicited AEs (i.e., reactogenicity parameters as defined in [Section 4.2.6](#)) will be recorded without attribution assessments by the subject on paper or an electronic diary card for 7 days after each injection. If the paper diary card is completed by subject, data will be transcribed by a clinician into the study database. Clinicians will follow and collect resolution information for any reactogenicity symptoms that are not resolved within 7 days.
- All unsolicited AEs will be recorded with attribution assessments in the study database from receipt of the first study injection through completion of the 4 week visit that follows each study injection. At other periods between injections and following the 4 week post-injection visit after the second vaccination through the last study visit, only SAEs ([Section 5.2](#)), new chronic medical conditions, and influenza or ILI will be recorded.
- Cases of influenza or influenza-like illness (ILI) will be evaluated as follows:
ILI is defined as fever (temperature of 100°F [37.8°C] or greater) and a cough and/or sore throat in the absence of a known cause other than influenza. Collection of nasopharyngeal swabs will be used for laboratory confirmation of influenza by polymerase chain reaction (PCR) in subjects who meet criteria for ILI. The severity of illness in subjects with laboratory confirmed influenza illness will be recorded on a case report form rather than on an AE form.

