6.2 ENDPOINTS

6.2.1 Primary Endpoints: Safety

Assessment of product safety will include clinical observation and monitoring of hematological and chemical parameters. Reactogenicity will be closely monitored for 7 days after each injection and safety evaluated by clinical visits for 52 weeks following the last vaccine administration and through an influenza season. See Section 4.2 and Appendix I for details and specified time points. The following parameters will be assessed for all study groups:

- Occurrence of solicited local reactogenicity symptoms for 7 days after each injection
- Occurrence of solicited systemic reactogenicity symptoms for 7 days after each injection
- Change from baseline in safety laboratory measures

- Occurrence of AEs of all severities through the 4 week post-injection visit
- Occurrence at any time throughout the study of SAEs or new chronic medical conditions that require ongoing medical management.

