6.4.3 Safety Analysis

6.5.3.1 Reactogenicity

The number and percentage of participants experiencing each type of reactogenicity sign or symptom will be tabulated by severity. For a given sign or symptom, each participant's reactogenicity will be counted once under the maximum severity for all assessments.

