APPENDIX I: SCHEDULE OF EVALUATIONS

	Visit Number	VRC 500	VRC 321 Schedule of Evaluations: Group 1											
			*01	02	02A	03	04	05	06	07	09	11	12	13
	Week of Study	-4 to 0		W0	W1	W1	W2	W4	W12	W16	W18	W28	W40	W52
	Day of Study	-28 to 0		D0	D1	D6	D14	D28	D84	D112	D126	D196	D280	D364
Clinical	Tube													
*VRC 500 Screening Consent		X												
VRC 321 AoU; Consent				X										
² Physical exam for eligibility, height /weight/ vitals at screening; vital signs and targeted exam (as needed) other visits.		X		X		X	X	X	X	X	X	X	X	X
Medical history targeted to eligibility at screening; then interim medical history		X		X		X	X	X	X	X	X	X	X	X
³ Study Product Administration: Group 1				X										
Phone evaluation (clinic visit as needed)					X									
Begin diary card				X										
⁴ Pregnancy test: urine or serum		X		X				X					X	X
⁴ Pregnancy prevention counseling/ Reproductive Information Form		X		X				X					X	X
CBC with differential	EDTA	3	3	3			3	3					3	3
Iron and serum ferritin		X						X						
Total bilirubin, AST, ALT, and ALP	GLT	4	4	4			4	4					4	4
Creatinine		X	X				X							
⁵ HLA type	EDTA											20		
HIV Ab/Ag Combo (other tests, if needed)	EDTA	3												
Research Samples														
H. pylori ferritin antibody and human ferritin antibody	SST	X						X						
Serum	SST	32	16	16		16	16	16	16	16	16	16	16	16
PBMC and plasma	EDTA	80	80			80	80	80	80	80	40	80	80	80
Daily Volume (mL)		122	103	0	96	96	103	103	96	96	56	116	103	103
Max. Cumulative Volume (mL)		122	225	225	321	321	424	527	623	719	775	891	994	1,097

* VRC 500: Screening evaluations must be no more than 28 days prior to Day 0 to be used for eligibility (negative pregnancy test from Day 0 must be used for eligibility). If clinical assessment on Day 0 suggests significant changes may have occurred since screening, then physical examination & laboratory studies done on Day 0 are used for eligibility.

¹ Day 0=day of enrollment and first vaccine injection. Day 0 evaluations prior to first injection are the baseline for assessing adverse events subsequently.

² Screening visit includes physical exam with vital signs. At other visits, physical exam is done if indicated. Otherwise only blood pressure (BP), pulse, temperature, and respiration are required.

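### Solicited systemic symptoms have no graded pre-injection record and no baseline rule, so complaints already present at injection count as reactogenicity in a primary endpoint

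*Combined protocol and SAP*

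**What the plan says.** - **Endpoint.** Section 6.2.1 lists five primary safety parameters. One is "Occurrence of solicited systemic reactogenicity symptoms for 7 days after each injection"; the local counterpart is another.
- **Collection.** Under Section 4.2.6 the diary is one "on which they can record temperature and symptoms daily for 7 days after each injection". Its systemic items are "unusually tired/feeling unwell, muscles aches (other than at injection site), headache, chills, nausea, joint pain", plus the day's highest temperature.
- **Attribution.** Section 5.1 says that solicited events "will be recorded without attribution assessments by the subject on paper or an electronic diary card for 7 days after each injection".
- **Counting.** In Section 6.4.3, under the subheading numbered 6.5.3.1, each participant's "reactogenicity will be counted once under the maximum severity for all assessments". Nothing there refers to the state before injection.
- **Design.** Section 4: "This is a Phase I, open-label, dose escalation study to evaluate the dose, safety, tolerability". The schema in Table 1 has no placebo or other concurrent control.
- **What exists before injection.** Section 4.2.5 requires a clinical evaluation on each injection day and allows rescheduling for fever or an acute illness that rules out vaccination. Appendix I schedules vital signs, including temperature, and an interim medical history at the injection visits. Footnote 1 in both schedules states: "Day 0 evaluations prior to first injection are the baseline for assessing adverse events subsequently".

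**The concern.** Headache, muscle aches, nausea and joint pain are non-specific and occur without vaccination. A control arm, an attribution step or a baseline comparison could each separate such complaints from vaccine effects. For the solicited systemic items the plan specifies none of them. The other primary safety components do have a filter: unsolicited events receive attribution (Section 5.1), and laboratory values are assessed as change from baseline (Section 6.2.1).

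The existing injection-day assessments do not close the gap. None requires the diary items to be elicited or graded on the diary scale, and no analysis rule uses what they record. Rescheduling would not catch a mild headache or long-standing joint pain. The footnote 1 baseline precedes the first injection only, so for the second dose it is 16 weeks old.

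At stake is an upward bias of unknown size in the systemic tolerability rate for a first-in-human product. The pre-injection state cannot be reliably recovered afterwards.

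**Working it through.** **1. The plan's own figures.** The plan states no expected rate, precision or power for reactogenicity, so there is no figure of that kind to reproduce. The related tables do reproduce. The exact (Clopper-Pearson) interval for 5 of 12 is 0.152 to 0.723, as in Table 6-2. Every off-diagonal cell of Table 6-3 matches by exact enumeration of two groups of 12 with a two-sided Fisher test at 5% (level and sidedness are not stated and are assumed here); for example 42% for 0.1 against 0.5, and 21% for 0.3 against 0.6.

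**2. Inputs for the bias.**
- Group size: 12 in each of 2A-2D, 48 combined (Section 6.3).
- t, the proportion with a vaccine-caused systemic symptom: not in the documents; assumed 20%.
- b, the proportion with a systemic complaint present at injection and then entered in the diary: not in the documents; assumed 5%, 10% or 15%.
- Independence of the two: assumed.

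**3. Formula and results, one 7-day window.** Observed rate = 1 − (1 − b)(1 − t).

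| b | Calculation | Observed | Excess over 20% | Expected extra of 12 | Expected extra of 48 |
|---|---|---|---|---|---|
| 0% | 1 − 1.00 × 0.80 | 20% | 0 points | 0 | 0 |
| 5% | 1 − 0.95 × 0.80 | 24% | 4 points | 0.48 | 1.92 |
| 10% | 1 − 0.90 × 0.80 | 28% | 8 points | 0.96 | 3.84 |
| 15% | 1 − 0.85 × 0.80 | 32% | 12 points | 1.44 | 5.76 |

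One subject is 1/12 = 8.3 points within a group.

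**4. Two doses.** The rule that each sign or symptom is "counted once under the maximum severity for all assessments" does not say whether this applies per dose. If a subject is counted once across both windows, background has two chances to enter. Holding t at 20% for the whole course and taking the two visits as independent, b = 10% gives 1 − 0.80 × 0.90² = 35.2%, against 28% for one window. Long-standing complaints would be correlated between visits, which puts the figure between the two.

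**5. Age groups.** Suppose, purely as an assumption, that b is 5% in 2A and 15% in 2D, with t = 20% in both. The observed rates are 24% and 32%, a gap of 8 points unrelated to the vaccine. By the enumeration in step 1, Fisher's test would reject in about 2.7% of trials. Group 2D would exceed 2A by three or more subjects in about 24% of trials, against about 11% with b = 5% in both. Such a gap could catch the eye in a table but would rarely be significant.

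**The case against.** **There is a pre-injection assessment.** A reader might infer that nothing about symptoms is recorded before injection. The documents do not support that: Section 4.2.5 and Appendix I provide an evaluation, vital signs and interim history. Section 5.1 also calls the diary items solicited AEs, so footnote 1 can be read as covering them. This stands. What is missing is item-by-item grading before each dose, and a rule that brings a baseline into the 6.5.3.1 table. Footnote 1 supplies neither.

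**An all-cause count is a legitimate endpoint.** Recording without attribution avoids subjective causality calls in an open-label study, and over-counting is the cautious direction in a first-in-human trial. This stands, and it is the reason to keep the all-cause table as the main count.

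**Not every item is affected.** Local items are tied to the injection site, and Section 4.2.5 has clinicians consider local problems when choosing the arm. The fatigue item is worded relative to the subject's usual state. The bias concerns mainly the other systemic items. Subjects are also selected for good general health, which should limit b.

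**No pause rule changes.** Section 4.5.1 excludes self-limited solicited reactogenicity from the pause criteria unless it is an SAE. This stands; the effect is on the reported rates.

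**Age effect.** A reader might infer that the plan will produce a false age trend in tolerability. The documents give no background rate by age and plan no age comparison of reactogenicity. The 2A-2D comparison in Section 6.3.3 concerns immunogenicity and is stated to be unpowered.

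**The earlier trial's rate.** It is tempting to put the 38.3% from the sponsor's earlier ferritin vaccine trial (Section 1.3.1) in as t. That figure is an observed occurrence rate, so any background is already in it, and adding b would count background twice.

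**Conclusion.** The point holds as a gap in collection and analysis, limited to the solicited systemic items. The direction of the bias is upward wherever a complaint present at injection is entered in the diary. Its size is not known from the documents. Under an assumed vaccine-caused rate of 20%, assumed backgrounds of 5% to 15% and independence, it is 4 to 12 points per window, or about half a subject to one and a half subjects in a group of 12; it is zero if b is zero. In a single group this is small beside the exact interval. In the combined 48 it is about two to six subjects. Any age pattern would be descriptive only. This is an inexpensive improvement to a primary endpoint and does not make the planned all-cause count invalid.

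**What to change.** 1. At the existing injection visits (Visit 02 for all groups, Visit 07 for Groups 2A-2D), record and grade the solicited systemic items on the diary scale before injection. Use the vital-sign temperature already scheduled.
2. In 6.5.3.1, keep the all-cause table as the main count. Add a new-or-worsened column, defined as a post-injection grade above the pre-injection grade for that dose.
3. State that reactogenicity by age group is descriptive.

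**Cost.** About a minute of subject time per injection visit, one added form row at each, and one table column.

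**Limits.** The added column can miss a true vaccine reaction of the same grade as a pre-existing symptom, so it must not replace the all-cause count. It removes only complaints already present at injection; new unrelated symptoms during the 7 days will still be counted, and without a control arm this remains.

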4.2.7 Follow-Up through End of Study

Group 1: Study follow-up will continue via clinical visits through 52 weeks after the study injection and through an influenza season.

Groups 2A, 2B, 2C, and 2D: Study follow-up will continue via clinical visits through 52 weeks after the last study injection and through an influenza season.

4.2.8 Mucosal Sample Collection

Throughout the study, nasopharyngeal swabs for diagnostic purposes will be requested from subjects who meet criteria for influenza-like illness (ILI) as defined in Section 5.1.

4.2.9 Blood Sample Collection

At intervals throughout the study, blood will be drawn for safety and immunologic assays. Blood will be drawn from the arm veins of subjects by standard phlebotomy procedures. Total blood volume drawn from each subject will not exceed the NIH CC guidelines.

4.2.10 Apheresis

Group 2 subjects will be offered apheresis as an optional procedure at Visit 09 in order to collect blood cells of special interest for research. The apheresis procedure will be carried out by trained Department of Transfusion Medicine (DTM) medical staff using automated cell separator devices.

Apheresis performed for this protocol will be performed solely for research purposes. All study subjects will be treated according to standard DTM whole blood and apheresis donation policies and procedures. Prior to the scheduling apheresis, the subject must have a venous assessment performed by the DTM staff.

In order to undergo apheresis procedures, a subject must meet the apheresis eligibility criteria as described in Section 4.2.11 and have no medical contraindications, as determined by the DTM staff. A VRC study clinician will complete a checklist for apheresis eligibility before referring a subject for the procedure.

Prior to beginning the apheresis procedure, a study clinician may request in advance that other laboratory samples be collected as needed to monitor the well-being of the subject or if needed by a research laboratory. In addition, for women of reproductive potential, a pregnancy test by blood or urine will be performed by a VRC study clinician within 72 hours prior to the apheresis procedure. Results must be negative to proceed with apheresis.

The Dowling Apheresis Clinic staff at the NIH CC routinely performs a hemoglobin test prior to initiating apheresis, per DTM Apheresis Clinic standard policies. If a subject is found to have a hemoglobin value less than permitted by the Apheresis Clinic, then the apheresis will not be initiated, and the ordering provider will be notified.

In this study, the procedure will require two antecubital venous access sites and will involve processing 1 to 4 liters of whole blood. The expected mononuclear cell yield is approximately 0.5 to 1.0×10^9 cells per liter processed, and the apheresis device can process about 2 to 3 liters per hour. Thus, 1 to 2 hours are required to process 1 to 4 liters of blood and obtain about 1 to 4×10^9 leukocytes. The packed red cell loss during the procedure is the equivalent of a 6 mL blood draw; this is the volume that will be used for the purposes of calculating cumulative blood draw when apheresis is performed.

During or following an apheresis visit, if there is any concern about the well-being of the subject, the DTM clinic may conduct appropriate medical evaluations by history-taking, physical examination, laboratory tests, and/or other testing.

Research blood samples will be processed and stored at VIP or a collaborating research laboratory. Stored samples may be used later to further evaluate immune responses and to elucidate genetic factors associated with immune response.

